OVERVIEW Adult men and women will be (50 kg), body mass index grea use of any Cannabis or canna experimental procedures in 15	invited to participate. Inclusion criteria will include iter than 25 kg/m ² , absence of any gastrointestin bis containing products for three days prior to eac adults.	e: age over 18 years, body mass greater than 110 Lbs nal or metabolic diseases, and ability to refrain from ch laboratory visit. The goal is to complete all
Following screening (i.e. med participants will report to the la morning having abstained from instrumented for measurement kept patent via a saline drip.	cal history, and assessment of body composition b on seven separate occasions separated by a n n food for 12-hours, and any products containing t of heart rate and blood pressure. A venous cath	via dual energy X-ray absorptiometry (DEXA)) ninimum of 4-days. Participants will arrive in the CBD for 72-hours. On arrival participants will be heter will be introduced to an arm or hand vein and
Two of the visits will begin wit 30 mg dose of CBD or a place circulating markers of carbohy analysis of blood for circulatin	n measurement of resting metabolic rate followed bo. Postprandial metabolism will be studied usin drate and fat metabolism. Blood will also be sam o markers of liver function	l immediately by ingestion of a liquid meal and a singl ng indirect calorimetry and repeated blood sampling fo npled for determination of CBD pharmacokinetics and

The other five visits will comprise ingestion of different CBD formulations without a meal. Venous blood will be sampled at

C -PROTOCOL	PROTOCOL IRB Form	Protocol # 21-10634H Date Printed: 03/24/2021
Protocol Title: Protocol Status:	Interaction between Cannabidiol, Meal APPROVED	Ingestion, and Liver Function
Date Submitted:	03/03/2021	
Approval Period:	03/24/2021-03/17/2022	
Important Note:	This Print View may not reflect all comment Please check the comments section of the Questions that appear to not have been an for this submission. Please see the system	ts and contingencies for approval. online protocol. swered may not have been required application for more details.
standardized intervals over 4-hours a	and will be analyzed for circulating CBD concentra	tion and markers of liver function.
DETAILS		
Visit 1: Screening Visit - Duration: ~ During this visit participants will com undergo basic measures of body cor DEXA). Body composition is a know metabolism. DEXA data will be used	0.5 hour plete the Informed Consent, provide a brief medica mposition (height, weight, and waist and hip circum n physiological regulator of CBD concentration, ar d as a statistical co-variable in our final analysis.	al history, and will nference, and nd is related to metabolic rate and postprandial
The remaining seven visits will occur but not the dose, of CBD. The other resting metabolism, ingestion of a m substitution of a placebo for CBD.	r in a random order. Five of these visits will be alm two visits will be almost identical to the other five l eal, measurement of metabolic rate following the n	nost identical, differing only in the preparation, but they will also include measurement of neal, and one of the visits will entail the
Five Visits Not Involving A Test Meal Participants will report to the lab on f having abstained from food for 12-ho for measurement of heart rate and b saline drip.	I ~ 4.5 hours each five separate occasions separated by a minimum o ours, and any products containing CBD for 72-hour lood pressure. A venous catheter will be introduced	of 5-days. Participants will arrive in the morning rs. On arrival participants will be instrumented d to an arm or hand vein and kept patent via a
Following baseline blood sampling (t standardized intervals over 4-hours: concentration. Each blood sample w	time 0), participants will ingest one of the product fo 0, 10, 20, 30, 45, 60, 120, 180, and 240 minutes a ill be ~5 mL.	ormulations. Venous blood will be sampled at and will be analyzed for circulating CBD
In addition, venous blood will also be including alanine aminotransferase (nitrogen. These samples will be take	e sampled and analyzed for circulating factors indic ALT), albumin, alkaline phosphatase, aspartate an en at time 0, 60 and 240 minutes. Each of these b	cative of liver (and also kidney) function, ninotransferase, total bilirubin, and blood urea lood samples will be ~1 mL.
The following formulations will be stu	udied. All products will be standardized to 30mg CE	BD per dose.
1)T-P-S-10 Caliper powder - 30 mg (2)Oil based tincture - 30 mg CBD isc 3)10% CBD Gum Arabic, maltodextr 4)10% CBD Gum Arabic, sorbitol ba 5)CBD Isolate in water	CBD in the form of 300 mg of 10% CBD isolate plate in MCT oil (1:1 ratio of CBD to MCT oil) in base se	
One of the non test meal visits, the v ingested will also involve additional k 10, 20, 30, 45, 60, 90, 120, 150, 180	risit in which T-P-S-10 Caliper powder - 30 mg CBI blood sampling for the measurement of glucose, in: 9, 210 and 240 minutes. Each of these blood samp	D in the form of 300 mg of 10% CBD isolate is sulin and triglyceride concentration at time -5, oles will be ~3 mL.
Two Visits Involving a Test Meal ~ 5. Participants will report to the lab on the having abstained from food for 12-hor for measurement of heart rate and be saline drip.	.5 hours each wo separate occasions separated by a minimum o ours, and any products containing CBD for 72-hour lood pressure. A venous catheter will be introduced	of 5-days. Participants will arrive in the morning rs. On arrival participants will be instrumented d to an arm or hand vein and kept patent via a
Resting Metabolic Rate (ventilated h pressure and heart rate will be meas	ood technique,indirect calorimetry) for 45 minutes sured.	and blood
Participants will ingest a meal. The r Nestle Health and Science, 15% DV 40% of RMR, resulting in a meal app 10-minutes. Immediately after the m of 300 mg of 10% CBD isolate).	meal will consist of a commercially available liquid carbohydrate, 5% DV fat, 20% DV protein). The to proximately equivalent to 30% of total daily caloric in neal, participants will ingest a placebo or CBD (T-P	mixed meal (Boost Balanced Nutrition Drink; otal number of calories will be the equivalent of requirements. The meal will be ingested within -S-10 Caliper powder - 30 mg CBD in the form
Immediately after the meal and CBD begin. Measurements lasting 25 mir minute measurement, the ventilated	ingestion, measurement of metabolic rate (ventila nutes will be performed at 0, 30, 60, 90, 120, 150, hood will be removed to provide the participant wit	ted hood technique, indirect calorimetry) will 180, and 210 minutes. At the end of each 25- th a 5-minute break.
Venous blood will be sampled at star analyzed for circulating CBD concen	ndardized intervals over 4-hours: 0, 10, 20, 30, 45, tration. Each blood sample will be ~5 mL.	, 60, 120, 180, and 240 minutes and will be
In addition, venous blood will also be including alanine aminotransferase (e sampled and analyzed for circulating factors indic ALT), albumin, alkaline phosphatase, aspartate an	cative of liver (and also kidney) function, ninotransferase, total bilirubin, and blood urea

	C-PROTOCOL	PROTOCOL IRB Form	Protocol # 21-10634H Date Printed: 03/24/2021
	Protocol Title: Protocol Status:	Interaction between Cannabidiol, Mea APPROVED	I Ingestion, and Liver Function
	Date Submitted:	03/03/2021	
	Approval Period: Important Note:	03/24/2021-03/17/2022 This Print View may not reflect all commer Please check the comments section of the Questions that appear to not have been ar for this submission. Please see the system	nts and contingencies for approval. e online protocol. nswered may not have been required n application for more details.
nitroge	en. These samples will be tak	en at time 0, 60 and 240 minutes. Each of these l	blood samples will be ~1 mL.
Blood 180, 2	sampling for the measuremer 10 and 240 minutes. Each of	t of glucose, insulin and triglyceride concentration these blood samples will be ~3 mL.	at time -5, 10, 20, 30, 45, 60, 90, 120, 150,
At the from a breakf	end of all of the visits particip a menu of a local vendor on Ca fast to the participant for enjoy	ants will be provided with a breakfast. They will be ampus West (e.g. Rocky Mountain Bagels). The r ment while in the lab.	e invited to select something of value up to \$ esearch staff will collect and deliver the
i)	Please take a moment to ide care or established practice	entify which procedures outlined above are experir for the condition or situation in this area.	nental and which are considered standard of
	All of the procedures are sta	andard research procedures, and all have been pr ls (please refer to protocols: 19-8667H, 20-10278	eviously approved by the IRB for currently H, 19-9577H, 17-7577H, 13-4282H, 10-2202
	09-1125H and 08-610H).		
Explain as well	09-1125H and 08-610H). who will conduct the procedu	ures, where, and when they will take place. Indicat nmitment for the study. Include how the data will b	e the frequency and duration of visits/session e collected (i.e. in person or online).
Explain as well The pr studen 5/21/20 All pro There each. time be	09-1125H and 08-610H). who will conduct the procedu as the subject's total time correcedures will be conducted b hts): [name] (CITI 8/19/20 019), [name] (CITI 20 coedures will take place in the will be eight visits. Visit 1 will The total time commitment for etween each visit and facilitati	ures, where, and when they will take place. Indicate nmitment for the study. Include how the data will b y the investigator ([name]) and/or by trained members 018), [name] (CITI, 7/17/2019), [name] 020) and [name] (CITI 8/20/2020), and [name] Human Performance Clinical Research Lab in the last up to 0.5 hours. Five of the visits will last 4.5 a participant will be up to 34 hours distributed over e flexible scheduling.	e the frequency and duration of visits/session be collected (i.e. in person or online). s of the research team (including staff and [name] (CITI 2/1/2018), [name] (CIITI [name] (CITI December 2020). Department of Health and Exercise Science hours each. Two of the visits will last 5.5 ho er approximately 10-12 weeks to allow lots o
Explain as well The pr studer 5/21/2 All pro There each. time be	09-1125H and 08-610H). who will conduct the procedu as the subject's total time cor rocedures will be conducted b hts): [name] (CITI 8/19/2) 2019), [name] (CITI 2/ 2019), [name] (CITI 2/ 201	ures, where, and when they will take place. Indicate mmitment for the study. Include how the data will b y the investigator ([name]) and/or by trained members 018), [name] (CITI, 7/17/2019), [name] 020) and [name] (CITI 8/20/2020), and [name] Human Performance Clinical Research Lab in the last up to 0.5 hours. Five of the visits will last 4.5 a participant will be up to 34 hours distributed over e flexible scheduling.	e the frequency and duration of visits/session be collected (i.e. in person or online). s of the research team (including staff and [name] (CITI 2/1/2018), [name] (CIITI [name] (CITI December 2020). Department of Health and Exercise Science hours each. Two of the visits will last 5.5 ho er approximately 10-12 weeks to allow lots o
Explain as well The pr studer 5/21/2 All pro There each. time bu i)	09-1125H and 08-610H). The who will conduct the procedures as the subject's total time con- procedures will be conducted b hts): [name] (CITI 8/19/20 2019), [name] (CITI 20 2019), [name] (CITI	ures, where, and when they will take place. Indicate mmitment for the study. Include how the data will b y the investigator ([name]) and/or by trained members 018), [name] (CITI, 7/17/2019), [name] 020) and [name] (CITI 8/20/2020), and [name] Human Performance Clinical Research Lab in the last up to 0.5 hours. Five of the visits will last 4.5 a participant will be up to 34 hours distributed over e flexible scheduling.	e the frequency and duration of visits/session be collected (i.e. in person or online). s of the research team (including staff and [name] (CITI 2/1/2018), [name] (CITI [name] (CITI December 2020). Department of Health and Exercise Science hours each. Two of the visits will last 5.5 hours er approximately 10-12 weeks to allow lots of e documentation of permission to use each
Explain as well The pr studer 5/21/2 All pro There each. time b i) For sch subject	09-1125H and 08-610H). The who will conduct the procedu as the subject's total time corrections of the subject's total time corrections will be conducted b this): [name] (CITI 8/19/2/ 2019), [name] (CITI 20 coedures will take place in the will be eight visits. Visit 1 will The total time commitment for the total time c	ures, where, and when they will take place. Indicate nmitment for the study. Include how the data will b y the investigator ([name]) and/or by trained members 018), [name] (CITI, 7/17/2019), [name] 020) and [name] (CITI 8/20/2020), and Han Human Performance Clinical Research Lab in the last up to 0.5 hours. Five of the visits will last 4.5 a participant will be up to 34 hours distributed over e flexible scheduling. sed are in the public domain or provide appropriate ass time is used, describe in detail the activities pla ated during the activities.	e the frequency and duration of visits/session e collected (i.e. in person or online). s of the research team (including staff and [name] (CITI 2/1/2018), [name] (CIITI [name] (CITI December 2020). Department of Health and Exercise Science hours each. Two of the visits will last 5.5 ho er approximately 10-12 weeks to allow lots o e documentation of permission to use each
Explair as well The pr studer 5/21/2 All pro There each. time bo i) For sch subject Not ap	09-1125H and 08-610H). The who will conduct the procedu as the subject's total time corrections of the subject's total time corrections will be conducted be trocedures will be conducted be the subject's total time conducted be the subject's total time conducted be will be eight visits. Visit 1 will The total time commitment for the total time commitment for the total time commitment for the scale. Indicate if the instruments us scale. Not applicable hool-based activities where class and nonsubjects will be located be be and the total time commitment be total total time commitment be total time commitment for the scale. Not applicable	ures, where, and when they will take place. Indicat miniment for the study. Include how the data will b y the investigator ([name]) and/or by trained members 018), [name] (CITI, 7/17/2019), [name] 020) and [name] (CITI 8/20/2020), and [name] Human Performance Clinical Research Lab in the last up to 0.5 hours. Five of the visits will last 4.5 a participant will be up to 34 hours distributed over e flexible scheduling. sed are in the public domain or provide appropriate ass time is used, describe in detail the activities pla ated during the activities.	e the frequency and duration of visits/session be collected (i.e. in person or online). s of the research team (including staff and [name] (CITI 2/1/2018), [name] (CIITI [name] (CITI December 2020). Department of Health and Exercise Science hours each. Two of the visits will last 5.5 ho er approximately 10-12 weeks to allow lots o e documentation of permission to use each
Explain as well The pr studer 5/21/2 All pro time b i) For sch subject Not ap State if section	09-1125H and 08-610H). The who will conduct the procedures will be conducted by the subject's total time con- procedures will be conducted by the subject's total time con- trocedures will be conducted by the subject's total time con- trocedures will take place in the will be eight visits. Visit 1 will The total time commitment for- tetween each visit and facilitate Indicate if the instruments using scale. Not applicable total time commitment be located total time commitment be located total place will be located total be total time commitment by the total time commitment by the t	ures, where, and when they will take place. Indicate nmitment for the study. Include how the data will b y the investigator ([name]) and/or by trained members 018), [name] (CITI, 7/17/2019), [name] 020) and [name] (CITI 8/20/2020), and Han Human Performance Clinical Research Lab in the last up to 0.5 hours. Five of the visits will last 4.5 i a participant will be up to 34 hours distributed over e flexible scheduling. sed are in the public domain or provide appropriate ass time is used, describe in detail the activities pla ated during the activities.	e the frequency and duration of visits/session e collected (i.e. in person or online). s of the research team (including staff and [name] (CITI 2/1/2018), [name] (CIITI [name] (CITI December 2020). Department of Health and Exercise Science hours each. Two of the visits will last 5.5 ho er approximately 10-12 weeks to allow lots o e documentation of permission to use each anned for nonsubjects and explain where both dures. Submit a debriefing script in attachme
Explair as well The pr studer 5/21/2 All pro There each. time b i) i) For sch subject Not ap State if section No dee	09-1125H and 08-610H). The who will conduct the procedures as the subject's total time controcedures will be conducted bents): [name] (CITI 8/19/2019), [name] (CITI 2019), [name] (CITI 2019	ures, where, and when they will take place. Indicate mmitment for the study. Include how the data will b y the investigator ([name]) and/or by trained members 018), [name] (CITI, 7/17/2019), [name] 020) and [name] (CITI 8/20/2020), and [name] Human Performance Clinical Research Lab in the last up to 0.5 hours. Five of the visits will last 4.5 f a participant will be up to 34 hours distributed over e flexible scheduling. sed are in the public domain or provide appropriate ass time is used, describe in detail the activities pla atted during the activities.	e the frequency and duration of visits/session be collected (i.e. in person or online). s of the research team (including staff and [name] (CITI 2/1/2018), [name] (CIITI [name] (CITI December 2020). Department of Health and Exercise Science hours each. Two of the visits will last 5.5 ho er approximately 10-12 weeks to allow lots of e documentation of permission to use each anned for nonsubjects and explain where bot dures. Submit a debriefing script in attachme
Explair as well The pr studer 5/21/2 All pro There each. time b i) i) For sch subject Not ap State if section No dec Will aud apes/p	09-1125H and 08-610H). The who will conduct the procedures as the subject's total time controcedures will be conducted be the system of the s	ures, where, and when they will take place. Indicate mmitment for the study. Include how the data will b y the investigator ([name]) and/or by trained members 018), [name] (CITI, 7/17/2019), [name] D20) and [name] (CITI 8/20/2020), and Ham Human Performance Clinical Research Lab in the last up to 0.5 hours. Five of the visits will last 4.5 f a participant will be up to 34 hours distributed over e flexible scheduling. sed are in the public domain or provide appropriate ass time is used, describe in detail the activities pla atted during the activities.	e the frequency and duration of visits/session be collected (i.e. in person or online). s of the research team (including staff and [name] (CITI 2/1/2018), [name] (CIITI [name] (CITI December 2020). Department of Health and Exercise Science hours each. Two of the visits will last 5.5 ho er approximately 10-12 weeks to allow lots o e documentation of permission to use each anned for nonsubjects and explain where bot dures. Submit a debriefing script in attachme

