03/18/2021	NEW FORM Comme Sent (Cvcle 1)	nts		
03/19/2021	NEW FORM Response	ses		
03/23/2021	NEW FORM Responses	ses		
03/24/2021	NEW FORM Comme Received (Cycle 2)	nts		
03/24/2021	NEW FORM Comme Received (Cycle 2)	nts		

Statistical Analysis Plan NCT04971837 04/01/2022

All data, unless otherwise stated, are presented as mean and standard deviation. Statistical analyses were performed using dedicated, commercially available software (SigmaStat for Windows 3.5, Systat Software, Inc., Chicago, IL, USA). Differences in pharmacokinetic parameters between CBD formulations for CBD, and the CBD metabolites were explored using one-way analysis of variance (ANOVA) with repeated measures. Tukey's tests were used to further examine the identified main effects. The thermic effect of food was examined using two-way ANOVA with repeated measures comparing energy expenditure across time for the two conditions (i.e., CBD and placebo); respiratory exchange ratio and circulating concentrations of glucose, insulin, and triglycerides were compared in the same way. The thermic effect of food was also examined by comparing the area under the curve (trapezoidal method). Circulating markers of liver and kidney function were compared across time and between CBD formulations using two-way ANOVA with repeated measures and post-hoc Tukey's tests when appropriate. Relations between circulating CBD concentrations and markers of liver and kidney function. The level of statistical significance was set at p < 0.05.

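### Visit order is random with no balancing described, and no SAP model has a visit term: with about 15 completers, any trend over visits costs precision

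*Combined protocol and SAP*

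**What the plan says.** Protocol, Procedures, DETAILS (after Visit 1): the seven experimental visits take place "in a random order. Five of these visits will be alm" (the extracted text breaks off mid-word). Five visits differ only in CBD preparation. The other two add a liquid meal, with CBD at one and placebo at the other. The protocol does not say how the order is generated or whether sequences are balanced or blocked.

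Protocol, Procedures, OVERVIEW: the goal is to complete all "experimental procedures in 15" adults. Subject Population (a-f) gives an enrolment of 25. The visits spread over roughly 10 to 12 weeks.

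SAP (dated 04/01/2022):
- Pharmacokinetic parameters are "explored using one-way analysis of variance (ANOVA) with repeated measures", with formulation as the factor.
- The thermic effect of food uses "two-way ANOVA with repeated measures comparing energy expenditure across time for the two conditions"; respiratory exchange ratio, glucose, insulin and triglycerides are handled the same way.
- Liver and kidney markers are "compared across time and between CBD formulations using two-way ANOVA with repeated measures".

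In the two-way models, time means minutes within a visit. No model contains visit number, period or sequence.

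**The concern.** This is a seven-period crossover whose analysis has no period term. Over 10 to 12 weeks, outcomes may shift with visit number, for example through weight or diet change or growing familiarity with the procedures. Random order does not make each condition fall equally often at each visit when there are only about 15 people. Some conditions will by chance sit earlier than others, and a trend over visits then moves the estimated differences between conditions from one possible allocation to the next. Without a visit term that variation stays in the comparison. At stake are the precision and power of the formulation comparisons and of the CBD-versus-placebo meal comparison.

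**Working it through.** The documents give no power calculation, variance or expected visit trend, so there is no figure of the plan's own to reproduce.

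**Inputs from the documents:** 7 visits in random order; 15 completers; 5 formulations compared by one-way repeated-measures ANOVA; 2 meal visits; alpha 0.05. **Assumptions:** each person's order is an independent random permutation; within-person SD is 1; the trend is linear at 0, 0.1, 0.25 or 0.5 SD per visit; for power, one of the five formulations differs by 1 SD.

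**1. Imbalance in visit position.** In a random permutation of 7, a condition's position has variance (7² − 1)/12 = 4, and two positions have covariance −4/6. The difference between two conditions in one person has variance 2 × 4 + 2 × (4/6) = 9.33. Over 15 people the SD of the mean difference is √(9.33/15) = 0.79 visits. In simulation the two meal conditions differ by 0.64 visits on average (95th percentile 1.53). The earliest and latest of the five formulations differ by 1.30 (95th percentile 2.13).

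**2. Order split for the meal pair.** 2 × P(Bin(15, 0.5) ≥ 10) = 2 × 4944/32768 = 0.302. A 10-5 split passes (10 − 5)/15 = one third of any first-to-second shift into the CBD-placebo difference.

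**3. Precision.** With a trend of b SD per visit, the SD of a pairwise difference is √(2/15 + b² × 9.33/15):
- b = 0: √0.1333 = 0.37
- b = 0.25: √(0.1333 + 0.0389) = 0.41
- b = 0.5: √(0.1333 + 0.1556) = 0.54 (simulated 0.55)

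**4. Validity of the SAP test under random order.** The simulated mean difference between conditions is about 0 at every trend (−0.02 to 0.01 SD). Type I error is 0.048 to 0.053. For contrast, one fixed order for everybody at b = 0.25 gives a bias of 1.0 SD and type I error 0.66.

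**5. Power for the five-formulation test** (simulation, 3,000 replicates per scenario):

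| Trend per visit | Random order, no visit term (n = 15) | Random order, visit term (n = 15) | Williams, no visit term (n = 14 / 15) | Williams, visit term (n = 14 / 15) |
|---|---|---|---|---|
| 0 | 0.77 | 0.72 | 0.72 / 0.75 | 0.72 / 0.74 |
| 0.1 SD | 0.75 | 0.70 | 0.70 / 0.73 | 0.71 / 0.74 |
| 0.25 SD | 0.65 | 0.72 | 0.56 / 0.62 | 0.71 / 0.76 |
| 0.5 SD | 0.41 | 0.71 | 0.18 / 0.23 | 0.72 / 0.75 |

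A second run gave 0.64 and 0.40 in place of 0.65 and 0.41. At 0.25 SD per visit, Williams sequences without a visit term have type I error 0.013 / 0.020; with the term it is 0.046 / 0.050.

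**6. Residual imbalance.** Fourteen Williams sequences give a mean-position difference of exactly 0. At n = 15 the range across the five formulations averages 0.34 visits, against 1.30 under random order.

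**The case against.** The strongest defence is that randomisation already does its job. Step 4 bears this out: no bias over allocations, and type I error at its nominal level, because visit variation also enters the residual error. A reader might infer that condition is confounded with visit number. The documents do not support that, since order is randomised for each person; real confounding would look like the fixed-order case. What remains is lost precision and the chance imbalance of the one allocation actually drawn.

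Three other stronger readings are tempting.
- **That the randomisation is simple and unrestricted.** The protocol says only that the order is random, and the attached scope of work is not visible. The supportable statement is that the method is not given. Steps 1 to 5 assume independent permutations, and some form of blocking would shrink the imbalance.
- **That balanced sequences would cure this at no cost.** Step 5 shows otherwise. Balancing without the visit term lowers power below the present plan when a trend exists. Fifteen is not a multiple of 14, and enrolling 25 for 15 completers allows for dropout that would disturb balance.
- **That the results are distorted by some definite amount.** The documents report no trend in any outcome. The ventilated hood is used only at the two meal visits, so getting used to it could affect that pair but not the formulation comparisons.

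Carry-over is a separate matter and was not simulated. The protocol has 72-hour abstention and a time-0 sample. Its minimum gap is 4 days in the OVERVIEW and 5 days in the DETAILS, which must be reconciled.

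The defence also has a fair point on cost: with no trend, or a weak one of 0.1 SD per visit, adding the visit term to the existing random order loses about five points of power.

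**Conclusion.** The point holds as a cheap improvement, not as an error that invalidates the analysis. No balancing is described, no model has a visit term, and with about 15 completers a noticeable chance imbalance in visit position is likely (SD 0.79 visits for a pair of conditions; 30% chance of a 10-5 or worse split for the meal pair). The harm is conditional on a trend. At 0.25 and 0.5 within-person SD per visit, power for a 1 SD formulation difference falls from about 0.77 to about 0.64 and 0.40. Balanced sequences with a visit term hold about 0.75 at n = 15 whether or not there is a trend. The imbalance figures need only the independent random order and 15 completers. The power figures also rest on the assumed trend and effect size, for which the documents offer no values.

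**What to change.** 1. **Add visit number (1 to 7) as a factor in every between-condition model.** This is the essential part. The SAP is written in the past tense, so data may already be collected; the term can still be added then. State that it is added whatever the observed trend, and report a table of condition by visit position.
2. **State how the visit order was generated.**
3. **If allocation is still open, draw orders from a seven-condition Williams set** (14 sequences, each condition equally often at each visit and equally often after each other condition), with a replacement participant taking over the vacated sequence. Do not do this without step 1, because the ANOVA then becomes conservative.

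**Cost:** no added visits or participants. The term takes six degrees of freedom. With no trend, power falls from about 0.77 to 0.70-0.72 if it is added to the existing random order, with almost no loss under balanced sequences. A 15th completer or dropout leaves slight residual imbalance. In the formulation ANOVA the error degrees of freedom go from 4 × 14 = 56 to 50. The meal pair bears more of the cost, from 14 to 8 for the condition contrast, and its power loss was not computed. There a single term for first versus second meal visit, costing one degree of freedom, is a reasonable alternative if specified in advance of the analysis.

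### Does the unnamed time zero for blood samples at the two meal visits spoil the fasting baseline or the CBD clock?

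*Combined protocol and SAP*

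**What the plan says.** The sampling rules are in the protocol under Procedures.

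- **Five visits without a test meal.** The baseline sample is time 0 and the product is swallowed after it: "time 0), participants will ingest one of the product" formulations. Zero is therefore pre-dose. At the visit with the T-P-S-10 powder, glucose, insulin and triglycerides are also drawn, starting at -5 minutes.
- **Two visits with a test meal.** Resting metabolic rate is measured for 45 minutes, and the liquid meal follows: "The meal will be ingested within" 10 minutes. CBD or placebo is taken straight after the meal. Calorimetry then begins, in 25-minute windows, the first labelled 0.
- **Blood at the meal visits.** CBD is drawn at 0, 10, 20, 30, 45, 60, 120, 180 and 240 minutes, and liver and kidney markers at 0, 60 and 240. Glucose, insulin and triglycerides are drawn "at time -5, 10, 20, 30, 45, 60, 90, 120, 150", then 180, 210 and 240, with no sample at 0. No series names its zero event.

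The same section describes the meal visits as nearly the same as the other five, apart from the metabolic measurements, the meal and the placebo. The SAP compares CBD with placebo across time by two-way repeated-measures ANOVA for energy expenditure, respiratory exchange ratio, glucose, insulin and triglycerides. It compares pharmacokinetic parameters between formulations by one-way repeated-measures ANOVA with Tukey tests.

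**The concern.** Zero comes before the dose at the fasted visits, but the only stated zero at the meal visits comes after both meal and dose. If the blood samples share the calorimetry clock, a sample labelled -5 can be drawn while the participant is drinking the meal, so it is not a fasting value. If blood zero is instead the start of the meal, the -5 sample is fasting, but the dose comes up to 10 minutes after zero and every CBD sample is labelled later than its true time since dosing.

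The effect of a meal on CBD pharmacokinetics is a stated purpose, and Tmax is one of the quantities that the background expects a meal to change. A timing offset at fed visits only would fall on that comparison. CBD samples are 10 minutes apart over the first half hour, so a 10-minute offset is one whole interval.

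**Working it through.** The plan gives no figure on this point to reproduce. The check is a timeline.

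**Inputs.** Meal duration m, with 0 < m ≤ 10 minutes (protocol; 10 is a maximum). Dose at the end of the meal (protocol). Time taken to swallow the dose is treated as nil (assumption).

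**Reading A: zero is after meal and dose, as for calorimetry.** Meal start is at -m, so the -5 sample is at m - 5 minutes from the first mouthful.

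| m (min) | -5 sample relative to meal start | Time since dose at nominal t |
|---|---|---|
| 4 | 1 min before | t |
| 5 | at the start | t |
| 6 | 1 min after | t |
| 8 | 3 min after | t |
| 10 | 5 min after | t |

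The CBD clock agrees with the dose throughout. With m ≤ 5 the -5 sample also precedes the meal or coincides with its start, so this one reading gives both a fasting baseline and an aligned clock.

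**Reading B: zero is meal start.** The -5 sample is fasting. Time since dose is t - m. With m = 10, nominal 10, 20, 30 and 240 minutes are 0, 10, 20 and 230 minutes after the dose. A true Tmax of 30, 45 or 60 minutes would be labelled 40, 55 or 70, an excess of 10/30 = 33%, 10/45 = 22% or 10/60 = 17%.

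**Reading C: the metabolic baseline is drawn before the meal and CBD is timed from the dose.** Neither fault arises. The protocol does not spell this out, and nothing in it rules it out.

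**Does visit length decide between A and B?** No. A needs 45 + 10 + 240 = 295 minutes and B needs 45 + 240 = 285. Both fit the 5.5 hours (330 minutes) allowed.

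**What each planned analysis is exposed to.**

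- *Energy expenditure and respiratory exchange ratio:* nothing. Calorimetry has its own stated zero, and a 45-minute resting measurement precedes the meal on any reading.
- *Glucose, insulin, triglycerides, CBD against placebo:* both visits use one schedule, so the offset is common unless meal duration differs by condition. The SAP compares values across time and specifies no change from baseline and no baseline covariate.
- *Fed against fasted CBD Tmax:* exposed under Reading B only.

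**The case for a change.** The strongest case for a change is that staff could follow the text faithfully and still time samples differently, and that the SAP does not mention actual sampling times. The common nominal times in the two blood series make a single clock the natural reading, and a single clock leads to A or B. The possible damage to Tmax can be put in numbers. With 15 participants, a paired t test at two-sided 0.05 and an assumed SD of the within-person Tmax difference of 15, 20 or 30 minutes, the non-centrality is 10/(SD/√15) = 2.58, 1.94 or 1.29. A purely artefactual 10-minute shift would then be declared significant in 67%, 44% or 23% of trials.

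The gap in wording stands. The numbers do not carry the conclusion, for four reasons.

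- They need Reading B, the slowest permitted meal for everyone, and SDs that the documents do not give. For a 5-minute shift they fall to 23%, 15% and 9%.
- The SAP specifies no paired fed-against-fasted test. If the fed visit joined the formulations as a sixth condition under Tukey's test (72% lower critical power is not implied; same SDs, 70 error degrees of freedom), the figures for 10 minutes become about 37%, 17% and 6%.
- Recorded Tmax can only be a scheduled time. In a one-compartment model with an assumed 120-minute half-life, a 10-minute delay leaves recorded Tmax unchanged for true peaks at 40, 55, 60 or 70 minutes. For a true peak at 30 it moves the record to 45.
- The mid-meal baseline and the shifted CBD clock belong to different readings, so their harms cannot be added.

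**Conclusion.** The zero event for blood at the meal visits is not named, but no change to the plan follows. The reading with most support in the text is zero at dosing, since calorimetry at the same visits uses it. On that reading, pharmacokinetic times are right and the only cost is a glucose, insulin and triglyceride sample at most 5 minutes after the first mouthful, and only when the meal lasts more than 5 minutes. That sample has the same place in the CBD and placebo visits and has no special role in the SAP analysis. A shift of up to 10 minutes in fed Tmax requires the meal-start reading and an analyst who ignores when the dose was swallowed. Timing pharmacokinetics from the dose and drawing the baseline before feeding are ordinary practice, and a trained team would fill the gap that way.

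This rests on two assumptions: that the team followed that practice, and that meal duration did not differ systematically between the CBD and placebo visits. The documents give no reason to doubt either.
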